7.1.1.5 Independent review, adjudication, and reliability (quality assurance)

All masked radiographs will be assessed independently by two blinded reviewers (musculoskeletal radiologist and orthopedic surgeon) using a pre-specified scoring manual. Reviewers will undergo a brief calibration exercise prior to study readings. Images will be presented in random order and without access to clinical data or treatment allocation.

Inter-rater reliability for mRUS will be quantified using appropriate agreement statistics (e.g., ICC for total mRUS and weighted kappa for ordinal cortex scores), and intra-rater reliability will be assessed by repeat scoring of a randomly selected subset of examinations after a washout period (e.g., 2–4 weeks), with re-randomization of the re-read set. Discrepant assessments of healing status relevant to the primary endpoint will be resolved by consensus; if consensus is not achieved, a third blinded reviewer will adjudicate. Reliability estimates will be reported with confidence intervals as part of study quality assurance.

7.2 Secondary outcomes

7.2.1 CORE-Kids outcomes

Marson et al. has developed the CORE-Kids core set of outcome domains for studies of childhood limb fractures [44]. These core outcomes are suggested to be included in all trials on childhood limb fractures to improve the consistency of research that can be combined for more meaningful meta-analyses and policy development.

The CORE-Kids outcome domains were agreed to include:

- Pain and discomfort
- Return to physical and recreational activities
- Emotional and psychosocial wellbeing
- Complications from the injury and its treatment
- Return to baseline activities daily living
- Participation in learning
- Appearance and deformity
- **Time to union – primary outcome**
- Recovery of mobility (for lower limb fracture)
- Recovery of manual dexterity (for upper limb fracture)

Another 5 outcomes were close to the consensus threshold:

- Cost to family

- Ability to sleep
- Range of motion
- The cost of treatment
- Child satisfaction

7.2.2 EQ-5D-Y - Patient reported outcome

To select an appropriate patient-reported outcome measure (PROM), we followed the recommendations of Marson et al. [52]. We selected the EQ-5D-Y questionnaire due to its ease of use, validated Danish translation, broad availability, use in prior research, and alignment with the intended secondary outcomes.

The questionnaire consists of the EQ-5D-Y descriptive system (index) and the EQ visual analogue scale (EQ VAS). The descriptive system comprises five dimensions:

- Mobility
- Looking After Myself
- Doing Usual Activities
- Having Pain or Discomfort
- Feeling Worried, Sad or Unhappy

Each dimension has three response levels: no problems/no pain/not worried, some problems/some pain/a bit worried, and a lot of problems/a lot of pain/very worried. Respondents indicate their health state by selecting the most appropriate response level for each dimension.

The EQ VAS is a 0–100 scale on which respondents rate their overall health on the day of questionnaire completion. It is conceptually different from the EQ-5D-Y index, which represents a value assigned to an EQ-5D-Y health profile using a set of weights reflecting population preferences for different health states. The EQ VAS reflects the respondent's perspective, whereas most value sets reflect a societal perspective.

For children aged 4–7 years, the proxy version will be used. A parent will complete the questionnaire based on their impression of the child's health status on the day of administration. For children aged 8 years and older, the self-reported version will be used.

The EQ-5D-Y has an official Danish translation and has been evaluated. Data will be collected using the REDCap self-report and proxy versions (Version 2.0). Administration and scoring will follow the EQ-5D-Y User Guide, Version 2.0 (September 2020).

The original English and Danish versions are provided as appendices.

7.2.3 Pain and discomfort

At each FU visit, pain and discomfort and use of medication is evaluated and documented.

7.2.3.1 Faces Pain Scale – Revised (FPS-R)

To measure the outcome of pain in children we use the Faces Pain Scale – Revised (FPS-R) [53]. It is a self-report measure of pain intensity developed for children. It was adapted from the Faces Pain Scale [54] to make it possible to score the sensation of pain on the widely accepted 0-to-10 metric. The scale shows a close linear relationship with numerical rating scales (NRS). It is easy to administer and

requires no equipment except for the photocopied faces (Figure 4). The child is asked to point to the face that shows how much pain the child is in at that moment. Faces are scored 0-10, where 0 equals no pain and 10 equals very much pain.

[figure not shown]

Figure 4 - Faces of the FPS-R. The child is instructed to point to the face that shows how much pain the child is in at that moment. Faces are scored 0, 2, 4, 6, 8 or 10 from left to right.

7.2.3.2 Discomfort

Pain and discomfort are domains in the EQ-5D-Y and is reported at each FU visit.

7.2.3.3 Pain medication

At each FU visit any use of pain medicine will be recorded.

7.2.4 Return to physical and recreational activities

Return to physical and recreational activity is described in the EQ-5D-Y. Return to sports will be documented in the eCRF.

7.2.5 Emotional and psychosocial wellbeing

Described by the domains of the EQ-5D-Y and the EQ VAS.

7.2.6 Complications from the injury and its treatment (adverse events)

This section describes all anticipated AEs, SAEs, ADEs, and SADEs. Further definition and description, see section 11.

7.2.6.1 Re-fracture, re-displacement, or re-angulation

At each FU the radiographs are reviewed for occurrence of re-fracture, re-displacement, or re-angulation. If changes are below the boundaries described in the inclusion criteria in 6.1.1 no additional treatment is necessary. If the boundaries are exceeded the PI and the surgeon will discuss the need for additional treatment.

7.2.6.2 Infection

Any surgery carries the risk of infection, however previous studies have shown very subtle infection risk [3,55] with the TEN procedure. We anticipate a risk of infection at 0.5%.

7.2.6.3 Nerve complications

Studies have shown a 5% risk of nerve injury [55], however all cases had spontaneous recovery of nerve function.

7.2.6.4 Re-operation

Re-operation risk is anticipated at 0.1-0.5% due for any reason following the procedure.

7.2.6.5 Discomforts/risks from casting

- Heat injury
- Pressure sores and skin breakdown
- Dermatitis
- Joint stiffness

7.2.6.6 Adverse Device Effects and Device deficiency

ADE and DD are defined in 11.1. Two cases of breakage of the Activa IM-Nail™ have been described. Steps to avoid ADE and DD have already been taken with revision of the Technique Guide. With the completion of our pilot study, we have gained valuable knowledge of the Activa IM-Nail™ procedure.

7.2.7 Return to baseline activities daily living

Described by the domains of the EQ-5D-Y.

7.2.8 Participation in learning

Partially described by the domains of the EQ-5D-Y and the EQ VAS. Return to school is entered in the eCRF.

7.2.9 Appearance and deformity

At each FU visit clinical adverse appearance or deformity is noted in the eCRF.

7.2.10 Recovery of manual dexterity / Range of motion

At each visit, sensory and motor nerve function is examined, and any irregularities are recorded in the eCRF.

Grip strength and bilateral elbow and forearm range of motion (ROM) is measured in degrees by goniometer and dynamometer, respectively.

7.2.10.1 Motor function assessment (MABC-3)

Motor function will be assessed using the Movement Assessment Battery for Children – Third Edition (MABC-3). MABC-3 is a standardized, age-normed performance-based test of motor coordination validated for children aged 3–16 years .

In this study, the Manual Dexterity domain will be used as an objective measure of upper-limb motor performance. The domain consists of age-appropriate, timed tasks assessing fine motor control, coordination, and precision of hand use. Tasks are selected according to predefined age bands (3–6, 7–10, and 11–16 years) and administered according to the standardized test manual.

Assessments will be performed by trained personnel at 12 weeks post-injury. Raw scores will be converted to age-adjusted standard scores and percentiles using normative reference data. The primary MABC-3 outcome will be the Manual Dexterity standard score, analyzed as a continuous variable.

MABC-3 was chosen to provide an objective, developmentally appropriate measure of functional motor recovery that complements radiographic healing, range of motion, grip strength, and patient-reported outcomes.

7.2.11 Cost to family

Days off work and days off school are recorded in the eCRF.

7.2.12 Ability to sleep

Any problems with sleep are addressed in the eCRF.

7.2.13 The cost of treatment

Treatment costs are discussed in 4.5.2. We intend to produce a cost-effectiveness analysis of the procedures involved.

7.2.14 Child satisfaction

Satisfaction of the child and parents are recorded using a questionnaire from the Danish Nationwide Survey of Patient Experiences (Landsdækkende Undersøgelse af Patientoplevelser - LUP) during the FU visit after 2 years. A copy (in Danish) is amended to the EC application.

7.3 Required diagnostic procedures

For diagnostic and follow-up purposes, plain radiographs of the forearm will be obtained at the following time points:

- At injury / preoperatively
- Intraoperatively (fluoroscopy)
- Postoperatively
- At follow-up (FU) visits until healing is established, but at a minimum at the 2-, 4-, and 6-week visits and possibly 8 and 10 weeks
- At FU visits after 12 weeks, 6 months, 1 year, and 2 years

8 Statistical planning

The statistical methodology for this clinical investigation—including definition of the primary estimand and analysis approach, justification of the non-inferiority margin, and the assumptions underlying the sample size and power calculations—was developed in collaboration with an independent statistician from the University of Copenhagen. The statistician contributed to the planning and validation of the statistical measures and will provide continued methodological support as needed during conduct and reporting of the study.

- Baseline characteristics and outcomes collected at scheduled follow-up assessments will be described using descriptive summary statistics.
- Categorical variables will be summarized as counts and percentages for each category.
- Continuous variables will be summarized using the mean, standard deviation (SD), median, interquartile range (IQR), and minimum and maximum values.
- When both baseline and follow-up measurements are available, continuous variables will additionally be summarized as within-patient change from baseline to follow-up.
- EQ-5D-Y results will be reported in accordance with the EQ-5D-Y user guide/manual.
- Adverse events (AEs) considered related to the study intervention will be summarized at the patient level. For summaries by severity, action taken, or outcome, patients experiencing more than one event of the same type will be classified according to the maximum severity and/or worst outcome observed.
- Analyses will be performed using validated statistical software (e.g., R/Stata/SAS and/or SPSS for descriptive analyses), as specified in the SAP.

When designing this non-inferiority study, we have considered the risk of “technocreep,” whereby successive non-inferiority trials may gradually erode the reference standard through incremental acceptance of smaller differences. For the present study, the non-inferiority margin is not derived from prior non-inferiority studies of the same implant type, thereby reducing the risk that margin selection is influenced by accumulated non-inferiority assumptions.

8.1 Non-inferiority hypotheses (primary estimand)

Let T denote time from surgery/randomization (Day 0) to radiographic union. Let θ denote the treatment effect expressed as the difference in time to union (BIN – TEN), in weeks. With a non-inferiority margin $\Delta = 3$ weeks, the hypotheses are:
 $H_0: \theta \geq \Delta$ (BIN is inferior to TEN by ≥ 3.0 weeks)
 $H_1: \theta < \Delta$ (BIN is non-inferior to TEN)

8.2 Sample size considerations

Sample size was calculated for a parallel-group, randomized (1:1), non-inferiority comparison of time to radiographic healing, defined as time from surgery/randomization to the first radiograph with mRUS ≥ 11 .

[figure not shown]

Figure 5 – Power table. To better appreciate the effects on sample size four standard deviations (SD) are plotted for five different power levels. The chosen SD and power are circled.

[figure not shown]

Figure 6 – Table to show sample size at 3 SD for 4 different non-inferior margins. The chosen margin and sample size are circled.

8.2.1 Power

To ensure a more reliable result, the power ($1-\beta$) is set to 90%.

8.2.2 Standard deviation

Due to limited evidence on the exact healing times of forearm fractures in children, the values are based on our pilot study, available literature [14,56] and our clinical expertise. In our pilot study of 18 fractures median time to healing with an mRUS of at least 11, was 8 weeks. We estimate that fractures heal to an mRUS of ≥ 11 at an average of 8 weeks with a SD of 3 weeks.

8.2.3 Significance level

Because a non-inferiority design is primarily investigating only one bound (lower or upper) of the confidence interval, we set a significance level (α) of 0.025 so that our one-sided test and upper confidence limit is comparable to results in two-sided superiority trials.

8.2.4 Non-inferiority margin

The primary objective is to demonstrate that bioabsorbable intramedullary nailing (BIN) is non-inferior to titanium elastic stable intramedullary nailing (TEN) with respect to time to radiographic union.

To support the choice of a clinically acceptable non-inferiority margin, we incorporated parent input from the pilot cohort. Parents were asked an acceptability question regarding the maximum additional weeks beyond the usual 6-week restriction for return to higher-risk activities (e.g., trampoline/contact sports) they would accept if their child could avoid a second operation for implant removal with bioabsorbable intramedullary nails. Responses were used to contextualize what families consider an acceptable trade-off and to ensure the non-inferiority margin is aligned with patient-relevant priorities, in addition to clinical judgement and the existing literature.

The non-inferiority margin is set at $\Delta = 3.0$ weeks, representing the largest clinically and parent acceptable delay in union for BIN compared with TEN.

8.2.5 Treatment effect (primary estimand)

The treatment effect will be expressed as the difference in time to union (in weeks):

$$\theta = T_{BIN} - T_{TEN}$$

where T denotes time from surgery date to radiographic union.

8.2.6 Drop rate / sample size inflation

In our pilot study, 1/18 (~5%) participants were lost to follow-up. For the present RCT we apply a total inflation of 10%, comprising ~5% loss to follow-up/withdrawal and ~5% intercurrent events affecting the primary endpoint (e.g., healing-related reoperation). Although intercurrent events will be handled in the primary estimand strategy (see Section 8.3), they reduce the number of informative observations for time-to-union and are therefore accounted for in the sample size inflation.

8.2.7 Sample size estimation

Sample size	
Significance level	0.025
Power (1-beta)	0.9
Ratio of sample size	1:1
Standard deviation	3 weeks
Non-inferiority margin	3 weeks
Loss to follow-up/withdrawal (%)	5
Intercurrent events (%)	5
Result	
Sample size per group	22
Sample size per group incl. attrition	25
Total sample size incl. attrition	50

Table 1. Results of sample size estimation.

To further strengthen robustness against uncertainty in the SD estimate, potential deviations from the assumed distributional model, and the possibility that a greater proportion of participants than anticipated may have non-informative primary endpoint data (e.g., due to intercurrent events), the study will enroll 30 participants per group (total $N = 60$). This provides additional precision for estimating the between-group difference in time to healing and ensures that the trial maintains at least the planned statistical power under plausible departures from the planning assumptions.

8.3 Statistical analysis

A detailed Statistical Analysis Plan (SAP) will be prepared for this study before the final analysis. An overview is presented in the following sections.

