6.2.17.2 Handling of data and missing assessments (interval-censored primary endpoint)

Data collected prior to discontinuation will be retained and used in analyses in accordance with applicable law and the scope of consent. If consent for use of data is withdrawn, previously collected data will be handled in accordance with regulatory requirements (e.g., retention of essential safety data where required) and the participant's stated wishes.

The primary endpoint (time to radiographic healing) will be analyzed as an interval-censored time-to-event outcome. For participants with radiographs demonstrating "not healed" followed by "healed," the event time will be considered to occur within the interval between the date of the last radiograph showing "not healed" and the date of the first radiograph showing "healed."

If a participant has no radiograph demonstrating healing, the observation will be right-censored at the date of the last evaluable radiograph/assessment.

If a participant undergoes reoperation, experiences refracture, or otherwise has a clinical course that precludes further valid assessment of healing, follow-up will be censored at the date of the last evaluable radiograph prior to that event, unless the event is pre-specified as a competing event in the Statistical Analysis Plan.

Assumptions and handling of missing radiographs (including sensitivity analyses for potentially informative missingness) will be pre-specified in the Statistical Analysis Plan.

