6.3.7 Blinding

Blinding is implemented to minimize performance and assessment bias [41–43]. Due to the nature of the interventions, the operating surgeon and operating room staff cannot be blinded to implant type.

Allocation is concealed from participants, parents, postoperative clinical staff, outcome assessors, and the statistician. A limited number of designated study personnel (e.g., PI and trial coordinator) are unblinded to facilitate device logistics and, when relevant, planning of elective titanium nail removal; these personnel will have no role in postoperative assessments, radiographic outcome evaluation, or data analysis.

Participant and parent unblinding will occur only after completion of the 6-month follow-up assessment, primarily to enable planning of elective removal of titanium nails in accordance with standard practice. All outcome assessors and the statistician will remain blinded until database lock and completion of the primary analysis, unless unblinding is required for patient safety.

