12.1 Data collection, source data, storage, and archiving

Data management will be performed by the Principal Investigator (PI). Data handling and protection will be conducted in accordance with ISO 14155, ICH-GCP, and applicable national and institutional regulations.

The study complies with the EU General Data Protection Regulation (GDPR) and Danish data protection legislation (Databeskyttelsesloven and Databeskyttelsesforordningen).

The electronic case report form (eCRF) will capture all study data for each participant, as specified in this CIP. Any modification of the eCRF will be made only if necessary and in accordance with an approved amendment to the CIP.

A minimal screening log will be maintained separately from the study database, as described in Section 6.1.4.1.

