19.1 Stopping rules

To identify potential safety signals or unexpected complications, an interim safety review will be performed after approximately 50% of the planned randomized participants have reached the 12-week follow-up visit (or have achieved radiographic healing, whichever occurs first).

The interim safety review will be conducted by the PI in collaboration with the sponsor and will include review of adverse events (AEs), adverse device effects (ADEs), serious adverse events (SAEs), serious adverse device effects (SADEs), and key clinical outcomes (refracture, deep infection, reoperation, loss of reduction, delayed union). If predefined stopping criteria are met, recruitment will be temporarily paused while the events are reviewed and appropriate actions are taken (including notification of the ethics committee, as applicable).

This interim review is for **safety monitoring only** (AEs/ADEs/SAEs/SADEs and prespecified healing-related safety signals including refracture and delayed healing) and is not a formal interim analysis of the primary noninferiority hypothesis; no early stopping for noninferiority/superiority efficacy is planned, and no alpha-spending adjustment will be applied based on this safety review.

Recruitment will be put on hold for safety reasons if at least one of the following incidents occurs and is assessed as possibly related to the investigational device (BIN):

- Refracture: An absolute refracture rate >25% (within the study follow-up period) will not be tolerated and will constitute a criterion for pausing recruitment.
- Delayed healing: An observed mean time to radiographic healing >12 weeks in the investigational (BIN) group will constitute a criterion for pausing recruitment.

After review, the sponsor and PI will decide whether recruitment can resume unchanged, resume with protocol modifications/risk-mitigation measures, or whether the study should be terminated.

20 Disclosures and economy

The initiative for this study has been taken solely by the authors.

The authors and affiliated colleagues have not received financial payments or other benefits from any commercial entity related to the subject of this study. The authors declare that they have no conflicts of interest.

Participants will not receive any financial compensation, gifts, or other economic benefits for participation in this study.

21 Deviations from the Clinical Investigation Plan

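### The SAP deadline in section 8.3 falls after the interim review that shows the PI and sponsor the BIN-arm healing times, so the few primary-analysis choices still open could be fixed with those data known

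*Protocol*

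**What the plan says.** Section 8.3 states: "A detailed Statistical Analysis Plan (SAP) will be prepared for this study before the final analysis". Section 23 places data analysis in 06.2031 to 12.2031. No section ties the SAP to first enrolment, the interim review, the unblinding of families at 6 months, or database lock.

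Section 19.1 schedules a look at the data part-way: "an interim safety review will be performed after approximately 50% of the planned randomized participants have reached the 12-week follow-up visit" (or have healed, if sooner). It also names the reviewers: "The interim safety review will be conducted by the PI in collaboration with the sponsor". The review covers adverse events and clinical outcomes including reoperation, refracture and delayed union. One of its two pause criteria is a mean time to radiographic healing above 12 weeks in the BIN group.

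On blinding, section 6.3.7 says: "A limited number of designated study personnel (e.g., PI and trial coordinator) are unblinded to facilitate device logistics". It adds that "these personnel will have no role in postoperative assessments, radiographic outcome evaluation, or data analysis" and that "All outcome assessors and the statistician will remain blinded until database lock and completion of the primary analysis". Section 12.1 gives data management to the PI.

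Section 6.2.17.2 censors a child at the last evaluable film before a reoperation or refracture, "unless the event is pre-specified as a competing event in the Statistical Analysis Plan". Section 8.3.6 calls the estimand scale pre-specified, but offers a time ratio and/or a model-based difference in medians only as examples.

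**The concern.** Pre-specification protects the error rate only if the specification precedes sight of the outcome. Here the stated deadline allows the reverse order: a review that must calculate the BIN mean of the primary endpoint comes first, and the document that settles the remaining analysis choices may come more than three years later. Nothing keeps the people who saw the interim data away from that document.

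At stake is whether the one-sided 2.5% level in section 8.3.1 can be defended. In a trial of 60 children, a choice about who counts as per protocol, or how the confidence limit is formed, can decide a result that lies near the margin. Even if nobody acts on the interim data, a reader of the final report could not verify that.

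**Working it through.** **1. Timing.** Inputs: first patient 05.2026 and data analysis from 06.2031 (section 23); recruitment of 36 months (6.1.4.7); review at about 50% of participants at 12 weeks (19.1). Assumption: even accrual.

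- Half randomised: 36 / 2 = 18 months.
- Plus 12 weeks: 12 / 4.345 = 2.8 months, so the review falls at about month 20.8, early 2028.
- May 2026 to June 2031 is 61 months, and 61 − 20.8 = about 40 months.
- If half are randomised by month 12 or by month 24 instead, the review falls at about month 15 or 27, and the gap is about 46 or 34 months.

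On each of these assumptions the review precedes the opening of analysis by years.

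**2. What the reviewers see.** About 30 of 60 children, so roughly 15 in the BIN arm. The 12-week criterion cannot be applied without calculating the BIN mean. No TEN mean is called for, but the planning mean of 8 weeks (8.2.2) is available for comparison.

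**3. What is already fixed.**

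| Element | Where | Status |
|---|---|---|
| Margin 3.0 weeks | 8.2.4 | fixed |
| One-sided 2.5%, upper 95% limit below 3.0 weeks | 8.3.1 | fixed |
| Per-protocol population primary | 8.3.2 | fixed |
| Weibull model; other distributions as sensitivity analyses | 8.3.6 | fixed |
| Censoring before healing-related reoperation | 8.3.8 | fixed as default |
| Missing films widen the interval; no imputation | 8.3.10 | fixed |

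**4. What is still open.**

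- *Summary of θ.* Sections 8.1 and 8.2.5 define a difference in weeks without saying mean or median, and 8.3.6 gives only examples. In the Weibull model with mean 8 and SD 3, the shape is 2.897, the scale 8.972 and the median 7.906. With a common shape, a mean difference of 3.0 weeks equals a median difference of 3.0 × 7.906 / 8 = 2.96 weeks. At the planning values this choice moves the estimate by only about 0.04 weeks.
- *Interval method.* Section 8.3.1 asks for a 95% interval but not how it is obtained (for example Wald or profile likelihood).
- *Competing events.* Section 6.2.17.2 lets the SAP override censoring; section 8.3.8 carries no such exception. Section 8.3.3.1(4) removes healing-related reoperation before union from the per-protocol set. In the primary analysis the exception therefore reaches little beyond cases such as a refracture without reoperation. It has more room in the supportive ITT analysis.
- *Per-protocol membership.* Sections 8.3.3 and 8.3.3.1 turn on whether follow-up films suffice, whether a deviation would materially affect the assessment of healing, and whether a cast deviation beyond 7 days was medically justified.

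**5. Rough size.** This uses the simple comparison of means behind the plan's sample size and ignores interval censoring. Evaluable children per arm: 30 × 0.9 = 27.

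- Standard error of the difference: 3 × √(2/27) = 0.82 weeks; half-width 1.96 × 0.82 = 1.60 weeks.
- The upper limit reaches 3.0 when the observed difference is 3.0 − 1.60 = 1.40 weeks.
- Excluding one child whose healing time lies 6 weeks (2 SD) from the arm mean shifts that mean by 6 / 26 = 0.23 weeks.

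One membership decision can thus reverse the verdict when the observed difference lies within about a quarter of a week of 1.40, but not when it is near zero.

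**The case against.** The case for leaving this alone is substantial. The core of the primary test stands in the protocol now. The statistician is blinded through the primary analysis, and section 8 says that an independent statistician helped to set the estimand and approach. Unblinded staff are barred from data analysis. The review is declared to be for safety only, and its healing criterion is one arm's mean in about 15 children. The SAP is not shown and may be finalised well before the outer limit in 8.3.

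Most of this stands, and it rules out several stronger readings that a reader might infer:

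- *That the authors could pick the best-fitting distribution after the fact.* Section 8.3.6 names Weibull as primary and the alternatives as sensitivity analyses, so an error rate calculated for a free choice among them would not describe this plan.
- *That the handling of missing films is open.* Section 8.3.10 settles the primary rule; what 6.2.17.2 defers adds assumptions and sensitivity analyses.
- *That a time ratio could replace the difference in weeks in the test.* Section 8.3.1 tests against 3.0 weeks, and no ratio margin is given.
- *That the PI and sponsor control the SAP.* No section says who writes or approves it. Section 6.3.7 does not list the sponsor as unblinded; its sight of the BIN mean follows only from 19.1.

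The objection does not close the gap. The bar on data analysis does not mention writing or approving the SAP, and the same PI manages the data and reviews healing outcomes. The safety-only statement excludes early stopping for efficacy, not knowledge of the data. A possible earlier SAP date does not amend a protocol that permits a late one.

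**Conclusion.** The point holds in a limited form. The stated SAP deadline is later than it should be, because it falls after a planned review in which an unblinded PI and the sponsor see the BIN mean of the primary endpoint. Under even accrual the gap is about 40 months (34 to 46 under the alternatives tried).

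The exposure is confined to the four open items above. The choice between mean and median is nearly immaterial at the planning values. Per-protocol membership can matter in a borderline result, at roughly 0.23 weeks for one child 2 SD from the arm mean. The effects of the interval method and the competing-event exception are not quantified here.

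No inflation of the type I error is demonstrated, and no sample-size figure changes. The conclusion rests on the absence of any rule on SAP authorship or approval in the protocol, and on the SAP itself not being available. Confidence is moderate; this is a worthwhile low-cost improvement, not a flaw that invalidates the design.

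**What to change.** Replace the deadline in section 8.3 with wording such as:

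> The SAP is finalised, signed and dated before the first participant is randomised, and at the latest before any healing data by arm are tabulated for the section 19.1 review. Later changes are made only by persons blinded to arm-level data, and are dated and justified.

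That SAP should name the summary of θ in weeks and the interval method, reconcile the exception in 6.2.17.2 with 8.3.8, and make the per-protocol judgement calls operational.

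The cost is that SAP writing moves forward, from as late as 2031 to before enrolment or, at the latest, before the interim review. No patients, visits or staff are added.
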